5.6 Data Analysis

Kinematic and kinetic data from the experiment will be processed in Visual 3D (C-Motion Inc., Germantown, MD) and aggregated using custom project specific software (Matlab; Mathworks, Natick, MA). To determine changes in walking performance, we will calculate biomechanical quantities related to body support, forward propulsion and balance control including: the vertical ground reaction force (GRF) impulse, the anterior GRF impulse, and the peak-to-peak range of the frontal and sagittal whole-body angular momentum. We will also calculate mechanical energy expenditure (i.e., the sum of the joint mechanical work of each leg). The GRF and joint work metrics will be normalized by body weight and added load while whole-body angular momentum will be normalized by body weight and added load, walking speed and leg length.

Linear mixed-effects regressions will be used to detect differences in the biomechanical quantities (dependent variables) between study prostheses (independent variables) for each load condition separately (anterior, posterior, intact-side carry, and prosthetic-side carry) following an assessment of normality. This method allows inclusion of subjects who do not complete all study procedures (repeated measures analysis of variance (ANOVA) models do not). These analyses will test for differences between the study prostheses across the four different load carriage conditions with random effects for subject and subject by study prosthesis interaction. If the data is not normally distributed, we will consult with our biostatistician on an appropriate transform. An omnibus test for significance will be generated using a likelihood ratio test with an alpha level of 0.05. Individual pair-wise differences will be assessed using simultaneous inference and associated 95% confidence intervals. All statistical analyses will be performed by study staff using existing VA enterprise software (SPSS Statistics v22; IBM, Inc.). Exact p-values will be reported for each test.

We conducted an exploratory power analysis for hypothesis **H1**. For this within-subject repeated measure study design, we used recently collected data (n=1) to compare potential differences across our study prostheses. When the subject walked at their self-selected speed with 13.6 kg added posterior load, the difference in vertical GRF impulse was 27.0 N*s/kg between two study prostheses with a mean standard deviation of 18.3 N*s/kg. We calculated 99 percent power to find a significant difference between the prostheses at $p<0.05$ for 20 subjects. For the anterior added load condition, the difference in vertical GRF impulse was 16.1 N*s/kg between two study prostheses with a mean standard deviation of 16.0 N*s/kg. We calculated 85 percent power to find a significant difference between the prostheses at $p<0.05$ for 20 subjects.

We also conducted an exploratory power analysis for hypothesis **H2**. When subjects walked at their self-selected speed with 13.6 kg added posterior load, the difference in the anterior GRF impulse was 1.8 ± 1.3 N*s/kg between two study prostheses. We calculated 98 percent power to find a significant difference between the prostheses at $p<0.05$ for 20 subjects. For the anterior added load condition, the difference in the anterior GRF impulse was 4.1 ± 2.4 N*s/kg between two study prostheses. We calculated 99 percent power to find a significant difference between the prostheses at $p<0.05$ for 20 subjects.

To aid in interpreting clinical meaning, we will calculate effect size (Cohen's *d* statistic) and will consider *d* values of 0.2, 0.5, and 0.8 to be small, moderate, and large effect sizes, respectively [33]. We will also interpret results relative to minimal detectable change criteria, when available, to ensure our statistical findings are clinically relevant.

Secondary Analyses

The satisfaction data from the experiment will be aggregated using project specific software (Matlab; Mathworks, Natick, MA). We hypothesize that there exists a study prosthesis that maximizes satisfaction across the different load conditions. The statistical analyses to test this secondary hypothesis will require a two-factor (prosthesis, load condition) Friedman analysis of variance (ANOVA). This analysis will test for differences between the four different study prostheses across the four different load conditions. The experiment-wise significance will be set a priori at an alpha level of $p<0.05$ and a Bonferroni adjustment will be applied for multiple comparisons. All statistical analyses will be performed using existing VA enterprise software (SPSS Statistics v22; IBM, Inc.). Exact p-values will be reported for each test.

Surface EMG data from the walking trials will be processed with existing custom algorithms in Matlab (Mathworks, Inc.). The collected data will be high-pass filtered (bidirectional Butterworth, 4th order, 50 Hz cutoff frequency), demeaned, and rectified, and then further smoothed using a Version 2.5; 5/14/2021 VA Puget Sound IRB Protocol Template – Version: 12/2015 Page **15** of **20**

moving root-mean-square (RMS) window of 80-ms. Subject average RMS profiles for each muscle at each condition will be normalized to the average peak RMS value of the same muscle for each stiffness setting while walking on the 0° condition. The kinematic and kinetic data will be filtered with a 4th-order Butterworth filter with cut-off frequencies of 6 Hz and 20 Hz, respectively, using Visual3D (C-Motion, Inc.). This data will be used to support the biomechanical observations.

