The aim of this research is to create guidance for VA clinicians who prescribe prostheses to veterans with a lower limb amputation who frequently carry infants, toddlers or other loads. To achieve this aim, we will conduct a human subject experiment with help of twenty individuals with below-knee amputations. Study participants will walk on a treadmill with no added load and four added load conditions using a weighted pack (13.6 kg or ~30 lbs) to simulate an infant, toddler, or other load. The four conditions include the pack strapped to their front, their back, and carried with their arms on the intact limb side and the prosthetic limb side. Each participant will wear a usual prosthetic foot, this same foot with a heel-stiffening wedge, the same prosthetic foot but one category stiffness higher, a new-to-market dual keel prosthetic foot intended for load carrying situations, and a powered ankle foot prosthesis. We will analyze the results of this experiment to determine which prosthetic foot (if any) and which load carrying condition (if any) is most advantageous.

List of Abbreviations

AE – adverse event
ANOVA – analysis of variance
ASIS - anterior superior iliac spine
CCTV - closed circuit television
CO - Colorado
CRQ – continuing review questionnaire
d – Cohen's *d* statistic
EMG – electromyography
GAS - medial gastrocnemius
GMAS - gluteus maximus
GMED - gluteus medius
GRF – ground reaction force
H – hypothesis
HAM - biceps femoris long head
HIPAA – health insurance portability and accountability act
IRB – institutional review board
ISO - Information Security Officer
Kg - kilograms
Lbs - pounds
M - Million
MA – Massachusetts
MD – Maryland
MIRB – Minneapolis Institutional Review Board
N - number of individuals
PHI – personal health identifiers
PI – principal investigator
PO – privacy officer
RF - rectus femoris
ROP – report of other problem
SA – specific aim
SAE – serious adverse event
SOL – soleus
SSWS - self-selected walking speed
TA - tibialis anterior
UW – University of Washington
VA – Veterans Affairs
VAPSHCS – Veterans Affairs Puget Sound Health Care System
VAS - vastus medialis
WA - Washington

Contents

Protocol Title: Load Carriage by Individuals with Lower Limb Amputation.....	5
1.0 Study Personnel.....	5
2.0 Introduction.....	5
3.0 Objectives.....	7
4.0 Resources and Personnel.....	8
5.0 Study Procedures.....	8
5.1 Study Design.....	8
5.2 Recruitment Methods.....	9
5.3 Informed Consent Procedures.....	12

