3.0 Objectives

The purpose of this research is to provide prosthesis prescription guidance for VA clinicians whose patients carry infants, toddlers, and other loads.

The specific aim of this research is to identify the study prosthetic foot that minimizes biomechanical gait deviations when compared to the standard-of-care for veterans with lower limb amputation who carry infants, toddlers, or other loads.

We will conduct a human subject experiment with unilateral transtibial amputees (n=40). Each participant will walk on an instrumented treadmill with no added load and four added load conditions of 13.6 kg: anterior, posterior, intact-side carry, and prosthetic-side carry. Using a

within-subject experimental design with block randomization, each participant will wear: a standard-of-care prosthetic foot, this same prosthetic foot with a heel-stiffening wedge, this same prosthetic foot but one category stiffer, a dual keel prosthetic foot intended for load carriage applications, and a powered ankle-foot purported to adapt to changing loads.

In general, we hypothesize that one of these prosthetic feet will minimize biomechanical deviations for (1) no added load, (2) anterior added load, (3) posterior added load, (4) intact-side carry load, and (5) prosthetic-side carry load.

Our specific hypotheses for each load condition are:

H1 a study prosthesis exists that maximizes the vertical GRF impulse (a measure of body support),

H2 a study prosthesis exists that maximizes the anterior GRF impulse (a measure of body forward propulsion),

H3 a study prosthesis exists that minimizes the peak-to-peak range of sagittal plane whole-body angular momentum (a measure of balance control primarily for anterior and posterior added load conditions),

H4 a study prosthesis exists that minimizes the peak-to-peak range of frontal plane whole-body angular momentum (a measure of balance control primarily for intact-side and prosthetic-side added load conditions), and

H5 a study prosthesis exists that minimizes the mechanical energy expenditure (allow for more efficient locomotion).

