Individuals with lower limb amputation may also be at a slight risk of injury (e.g., arising from a trip, a fall, or failure of the study prosthesis) or discomfort while they wear the study prostheses. The study prosthesis may have properties that are different than their as-prescribed prosthesis. As per clinical practice, subjects will be instructed to exhibit caution while acclimating to the study prosthesis. This is the same instruction provided when a veteran receives a new prosthetic component as part of a clinical prescription. Subjects will be asked to contact the PI or study staff in the event of any study-related pain or injuries to schedule an examination

The study population will be individuals with unilateral transtibial amputations. We anticipate approaching up to 500 individuals to enroll up to 40 individuals.

Vulnerable populations will not be specifically targeted for enrollment.

This study will not include specimen banking.

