## Statistical Analysis Plan

Outcome metrics: vertical GRF impulse, anterior GRF impulse, peak-to-peak range of sagittal plane whole body angular momentum (WBAM), and peak-to-peak range of frontal plane WBAM.

Linear mixed effects regression was used to assess differences in biomechanical outcomes (the dependent variable) by foot type for each load by combining all loading conditions in a single model and using a foot type by load condition interaction to estimate means and mean differences in outcomes by foot for each load separately. This model assumes a common variance in outcomes across load and foot. Thus, standard errors for the means will be similar across load and foot. Subject and foot type within subject were considered random effects. Several random effects structures were considered (from subject ID intercept only to a full subject by foot interaction model) with the best model chosen based on likelihood ratio tests. Hypothesis testing for the overall association between outcome and foot type were carried out using conditional F-tests for each load type. For comparison, the Benjamini Hochberg (BH) adjustment was also applied to the F-tests for each model across the 5 load conditions to maintain a false discovery rate of 5%. Hypothesis testing for pairwise differences across feet was carried out using Tukey's method to account for the inflation of the Type 1 error due to assessment of 10 pairwise differences for each load. Analyses were carried out using R 4.2.3 (R Foundation for Statistical Computing, Vienna, Austria) and packages tidyverse, lme4, emmeans and lmerTest.

Outcome metrics: positive net ankle joint work.

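### The 85% power stated for H1 under anterior load is for one unadjusted pair of feet; under the specified simultaneous inference it is about 65% at n=20, and the planned size is given as both 20 and 40

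*Protocol*

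**What the plan says.** The only sample-size reasoning in either document is the exploratory power analysis in Protocol section 5.6. It gives four powers, all for 20 subjects at p<0.05 and all for a difference between two prostheses. They are 99% (H1, posterior load), 85% (H1, anterior), 98% (H2, posterior) and 99% (H2, anterior). The 85% reads: "We calculated 85 percent power to find a significant difference between the prostheses at" p<0.05.

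The source for H1 is disclosed: "For this within-subject repeated measure study design, we used recently collected data (n=1) to compare potential differences across our study prostheses". For H2 no pilot size is given, and the posterior-load input is written as "the difference in the anterior GRF impulse was 1.8 ± 1.3 N*s/kg between two study prostheses".

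On the pairwise analysis, the same section says "Individual pair-wise differences will be assessed using simultaneous inference and associated 95% confidence intervals", without naming a method. The SAP uses "Tukey's method to account for the inflation of the Type 1 error due to assessment of 10 pairwise differences for each load", and its second part, on ankle joint work, repeats this.

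On size, the Protocol's opening summary says "we will conduct a human subject experiment with help of twenty individuals with below-knee amputations". Section 3.0 says "We will conduct a human subject experiment with unilateral transtibial amputees (n=40" in parentheses. Section 5.1 says "We anticipate approaching up to 500 individuals to enroll up to 40 individuals".

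**The concern.** The power statements describe a test that the plan does not use for pairwise differences. A comparison of two feet at an unadjusted 0.05 has a lower critical value than the same comparison judged within a family of 10, so the stated powers are too favourable for the planned pairwise rule. This matters most where the assumed effect is smallest relative to its SD, which is H1 under anterior load.

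The hypotheses ask which foot maximizes or minimizes an outcome. An overall test can show that the feet differ, but only the pairwise comparisons can say which one is better. A reader who takes the 85% at face value would believe that the anterior-load comparison clears 80% when, on the same inputs, it does not at 20 completers. The reader also cannot tell whether 20 or 40 is planned, and that decides whether there is a shortfall at all.

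**Working it through.** **Inputs (Protocol section 5.6).** Difference and SD, in N*s/kg: H1 posterior 27.0 and 18.3; H1 anterior 16.1 and 16.0; H2 posterior 1.8 and 1.3; H2 anterior 4.1 and 2.4. n = 20, alpha = 0.05. Two-sided testing is assumed, as the text does not say.

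**Step 1: reproduce the stated powers.** Treat each SD as a per-foot SD with zero correlation between feet within a subject. The SD of the paired difference is then SD × √2, and the noncentrality is (difference/SD) × √(n/2). For H1 anterior this is (16.1/16.0) × √10 = 3.18. The test is a paired t-test on 19 df with critical value 2.093.

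| Scenario | Difference/SD | Power, one unadjusted pair | Stated |
|---|---|---|---|
| H1 posterior | 1.475 | 99.3% | 99% |
| H1 anterior | 1.006 | 85.5% | 85% |
| H2 posterior | 1.385 | 98.6% | 98% |
| H2 anterior | 1.708 | 99.9% | 99% |

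Other readings of the H1 anterior inputs do not fit. Taking 16.0 as the SD of the difference gives 98.9%, a two-sample t-test with 20 per group 87.3%, and two groups of 10 56.7%.

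**Step 2: apply the specified pairwise rule.** Keep the same noncentrality and replace the critical value by Tukey's, q(0.95; k, df)/√2 with df = (k − 1)(n − 1).

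- Five feet, n=20: df = 76, critical value 2.794.
- Four feet (the list in Protocol section 5.5), n=20: df = 57, critical value 2.646.
- Five feet, n=40: df = 156, critical value 2.760.

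| Scenario | Five feet, n=20 | Four feet, n=20 | Five feet, n=40 |
|---|---|---|---|
| H1 posterior | 96.7% | 97.6% | >99.9% |
| H1 anterior | 65.1% | 70.2% | 95.8% |
| H2 posterior | 94.0% | 95.5% | >99.9% |
| H2 anterior | 99.5% | 99.6% | >99.9% |

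A simulation of H1 anterior (40,000 runs) gave 65.0% at n=20 and 95.7% at n=40.

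**Step 3: completers needed for H1 anterior under Tukey, five feet.** n=26 gives 79.98%, n=27 gives 81.9%, n=28 gives 83.6% and n=29 gives 85.3%. So 27 are needed for 80% and 29 to keep 85%.

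**Step 4: detectable difference.** With Tukey over five feet, 80% power requires a paired standardized difference (difference divided by the SD of the difference) of 0.816 at n=20 and 0.570 at n=40. At SD 16.0 and zero correlation these are 0.816 × 16.0 × √2 = 18.5 and 0.570 × 16.0 × √2 = 12.9 N*s/kg. The pilot difference of 16.1 lies between them.

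**Step 5: how far the inputs can be trusted.** One subject cannot supply the between-subject SD of a difference between feet. The ranges below are assumptions, for H1 anterior under Tukey over five feet.

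| Assumption | n=20 | n=40 |
|---|---|---|
| SD 2 times the pilot value | 12% | 31% |
| SD 1.5 times | 26% | 60% |
| As stated, zero correlation | 65% | 96% |
| Between-foot correlation 0.3 | 84% | >99% |
| SD 0.75 times | 92% | >99% |
| Between-foot correlation 0.5 | 95% | >99% |

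A positive correlation does not rescue the 85% itself. At correlation 0.3 the unadjusted power would be 95%, so the stated figure fits only zero correlation.

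**Step 6: the H2 ± notation.** If 1.3 is the SD of the difference, as the sentence reads, the paired standardized difference is 1.385 and power at n=20 is above 99.9%, not 98%. The 98% follows only if 1.3 is a per-foot SD with zero correlation.

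**The case against.** The strongest reply is that nothing is miscalculated. The section calls itself exploratory, discloses the single pilot subject, and says that the power is for two prostheses at p<0.05. It does not claim power after adjustment. This stands as far as it goes: the 85% is correct for the test it describes. But that is not the test the same section specifies for pairwise differences, and the label does not remove the mismatch.

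A second reply is that H1 is tested first by an overall test, for which the 65% is not the power. On the same inputs with five feet and n=20, the overall F-test has about 69% power if the other three feet lie midway between the pair, 90% if one foot differs from the other four by 16.1, and 98% if two feet differ from three. These figures are right, and they show that the shortfall for the overall question may be clear or absent. The protocol, however, states its power for a pair of feet, so the pairwise rule is the proper comparator.

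Third, the Protocol does not name Tukey; the SAP does. Other simultaneous methods do not help: Bonferroni over 10 pairs gives 52% to 65% at n=20, depending on the degrees of freedom. Larger degrees of freedom from the SAP's pooled model would raise the Tukey figure only to about 67%.

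Fourth, an enrolment of up to 40 could be a ceiling above a target of 20. That reading works for section 5.1, but section 3.0 gives 40 as the size of the experiment.

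**Conclusion.** The concern holds. On the protocol's own inputs, pairwise power for H1 under anterior load falls from 85% to about 65% at 20 completers once the specified simultaneous inference is applied, and to 70% if only four feet are compared. The loss is material in this one scenario of four. Separately, the documents contradict themselves on the planned size (20 or 40), and this decides whether the shortfall exists: 65% against 96%.

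The 65% assumes a per-foot SD of 16.0, zero between-foot correlation and Tukey over five feet. It measures the cost of multiplicity and is not an estimate of the study's true power, which one subject's data cannot give in either direction. The missing H2 pilot size and the undefined ± are gaps in detail that the conclusion does not depend on. This should be fixed, but it does not invalidate any planned test or estimate.

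**What to change.** In Protocol section 5.6, replace or supplement the four percentages with a statement of sensitivity on the planned test. For example: with Tukey adjustment over 10 pairs per load, the study has 80% power for a paired standardized difference of 0.82 with 20 completers (0.57 with 40). Add that the H1 pilot, being one subject, gives no between-subject SD. Give the pilot size for H2, and say whether each ± is a per-foot SD or the SD of the difference. State one planned number of completers in the opening summary, section 3.0 and section 5.6, and call 40 an enrolment ceiling if that is what is meant.

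The cost is protocol wording, plus a less favourable stated power for H1 anterior if 20 is the planned size. No test, estimate or participant number has to change.

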16 kg [9]. Approximately 14% of all civilian jobs had a strength level of “heavy work”, defined as occasionally carrying 23 to 45 kg, frequently carrying 12 to 23 kg, or constantly carrying items of 4.5 to 11 kg or less [10]. Among occupations, heavy work accounted for 46% of jobs in construction and extraction, 35% of jobs in installation, maintenance, and repair, 32% of jobs in transportation and material moving, and 22% of jobs in healthcare support [10]. Fully 45% of civilian jobs had a “medium work” level, defined as occasionally carrying 10 to 23 kg, frequently carrying 5 to 11 kg, or constantly carrying items of 5 kg or less [10].

Not surprisingly, individuals with lower limb amputations respond to load carriage conditions with greater metabolic costs [11] and asymmetric biomechanical deviations such as increased intact limb joint power generation and absorption and greater dorsiflexion of their prosthetic foot in late stance [12]–[14]. As discussed in the recent work by Koehler-McNicholas [15], this greater dorsiflexion of prosthetic feet is in stark contrast to the unaltered kinematics of the ankle-foot motion in non-amputees and suggests a significant short-coming in these devices. During added load conditions, a prosthetic foot with greater stiffness would be clearly desirable [16], but this benefit would be offset in the no load condition because the energy storage and release function, which facilitates locomotion, is reduced [17].

[figure not shown]

Fig. 1: Load carriage techniques.

While the biomechanical deviations depend on load magnitude and carriage technique, the negative consequence of load carriage include injuries such as foot blisters, pain and inflammation of the foot, knee and back, and stress fractures [5]. Individuals with vulnerable limbs due to trauma or diabetic/dysvascular etiologies are hypothesized to be at even greater risk for these common injuries.

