Using the same methods as the first study visit, subjects will be blinded to and fit with each study prosthetic foot in random order. After the first study prosthesis is fit, subjects will walk on our existing instrumented treadmill (AMTI, Watertown, MA) their SSWS determined during the first study visit. In random order, subjects will be asked to walk for one minute with no load and the four added load conditions. Kinematic and kinetic biomechanical data will be collected during each one-minute trial using a 12-camera Vicon system (Vicon, Centennial, CO) and two force plates embedded in the split-belt treadmill. Rest breaks will be provided as needed. After each load condition, we will ask the subject to rate their satisfaction with the functional performance of the study prosthesis using an 11-point Likert scale (0-10) where 0 is defined as completely dissatisfied and 10 as completely satisfied. Subject participation in the study will conclude after they have worn all four study prostheses.

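### The planned satisfaction test names four load conditions, but participants walk under five and, on the natural reading, rate all five, so the comparison of feet without load is left out

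*Protocol*

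**What the plan says.** **Collection.** Protocol 5.5 (Experimental Protocol) says of the second visit: "In random order, subjects will be asked to walk for one minute with no load and the four added load conditions". The rating instruction follows in the same paragraph: "After each load condition, we will ask the subject to rate their satisfaction with the functional performance of the study prosthesis", on a 0 to 10 scale.

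**Objectives.** Protocol 3.0 puts no added load first of five conditions: "for (1) no added load, (2) anterior added load, (3) posterior added load, (4) intact-side carry load, and (5) prosthetic-side carry load". It then introduces the specific hypotheses as applying to each load condition.

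**Analysis.** For the biomechanical outcomes, Protocol 5.6 fits models "for each load condition separately (anterior, posterior, intact-side carry, and prosthetic-side carry"; no load is not in that list. For satisfaction, the Secondary Analyses part of 5.6 hypothesises that some study foot gives the highest satisfaction over the load conditions. It plans a two-factor Friedman analysis (prosthesis, load condition) and adds: "This analysis will test for differences between the four different study prostheses across the four different load conditions". Alpha is 0.05 experiment-wise with a Bonferroni adjustment.

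**SAP.** The block on GRF impulses and angular momentum refers to 5 load conditions and 10 pairwise differences per load. The block on ankle joint work combines all loads. Neither lists satisfaction.

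**The concern.** Satisfaction is meant to inform which foot to prescribe, and a prescribed foot is worn with and without a load. Protocol 2.0 explains why the unloaded state is of interest. It calls greater stiffness desirable under added load, but says "this benefit would be offset in the no load condition because the energy storage and release function, which facilitates locomotion, is reduced". Several of the study feet differ from the standard foot by added stiffness, so the no-load walk is where that trade-off would be seen.

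Under the rule as written, the satisfaction test would look only at loaded walking. A foot could come out best under load, and the planned test would not say whether participants also preferred it, or disliked it, without load. The biomechanics would be reported at five conditions and satisfaction at four, from the same walking trials, with no reason given for the difference.

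**Working it through.** The plan gives no sample size, power or error calculation for satisfaction, so there is no figure to reproduce. The check is a count.

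**1. Conditions walked.** 1 (no load) + 4 (added loads) = 5 (Protocol 5.5; the same five in 3.0 and 5.1).

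**2. Conditions rated.** The rating instruction covers each load condition and comes just after the five are listed. Three places support reading no load as one of them:
- 2.0 uses the term for the no-load state.
- 3.0 counts it as item (1).
- The first-visit text in 5.5 lists no added load and the added loads, then refers to them together as all load conditions.

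On that reading, 5 are rated per foot.

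**3. Conditions analysed.** 4 (Protocol 5.6, Secondary Analyses). The list earlier in 5.6 shows that these are anterior, posterior, intact-side and prosthetic-side carry.

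**4. Share left out.** (5 − 4)/5 = 1/5 = 20% of ratings per foot.

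| Study feet | Rated per participant | Analysed | Left out |
|---|---|---|---|
| 4 (5.6 Secondary Analyses; 5.5) | 4 × 5 = 20 | 4 × 4 = 16 | 4 |
| 5 (protocol summary; 3.0; 5.1) | 5 × 5 = 25 | 5 × 4 = 20 | 5 |

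The SAP's 10 pairwise differences agree with five feet, since 5 × 4/2 = 10.

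**5. Effect on multiplicity.** The plan does not define the Bonferroni family. If every pair of feet is tested within every load, the number of tests is (pairs of feet) × (loads):
- Four feet, 6 pairs: 6 × 4 = 24 rises to 6 × 5 = 30. Per-test alpha goes from 0.05/24 = 0.00208 to 0.05/30 = 0.00167.
- Five feet, 10 pairs: 10 × 4 = 40 rises to 10 × 5 = 50. Per-test alpha goes from 0.05/40 = 0.00125 to 0.05/50 = 0.00100.

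**6. Whether pooling five conditions is enough.** Take a hypothetical pair of feet, A and B, ranked within each load (2 = preferred). A is preferred under all four added loads and B without load.
- Four loads: A = 4 × 2 = 8, B = 4 × 1 = 4.
- Five conditions: A = 8 + 1 = 9, B = 4 + 2 = 6.

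A leads either way. A pooled rank test can hide the reversal, so the no-load comparison has to be shown separately.

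**The case against.** **The no-load rating is inferred.** No sentence says outright that satisfaction is rated without load, and 5.6 uses the term load condition for the four added loads alone. This stands as a limit. If no such rating is taken, nothing is discarded; the gap is then in data collection, and closing it takes more than an edit. The no-load result is missing in either case.

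**Restriction to loads is defensible.** The specific aim concerns veterans who carry loads, the five-item list in 3.0 is about biomechanical deviations, and nothing forbids a descriptive report of no-load ratings. This is fair, but the plan gives no such reason, and the SAP did not keep the four-load restriction for the outcomes it covers.

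**The sentence may simply be out of date.** It also says four prostheses where other sections say five. That weakens any reading of a deliberate exclusion, but it remains the only rule for this endpoint.

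**A stronger reading that a reader might infer** is that the plan biases the satisfaction result toward stiffer feet by its own reasoning. The documents do not support this. The passage in 2.0 is about energy storage and release, not satisfaction. It says a benefit is offset, not that the ranking of feet changes or that users dislike a stiffer foot. The argument also does not reach every foot equally: 2.0 describes the dual keel as becoming stiffer as load is added, and 3.0 describes the powered foot as purported to adapt to load. It applies mainly to the stiffer-category foot and, at the heel, to the wedge.

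**Conclusion.** The mismatch is real and worth correcting, at modest weight. As written, the satisfaction test omits one of the five conditions walked, and with it 20% of the ratings per foot. It therefore cannot show whether a preference under load carries over to unloaded walking.

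This rests on two readings: that a rating is taken after the no-load walk, and that the four conditions in the satisfaction sentence are the four listed earlier in 5.6. Both are the natural reading, and the first is not stated outright. Extending the functional trade-off in 2.0 to satisfaction is an inference. It gives a reason to look at the no-load ratings but does not predict what they will show.

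The endpoint is secondary. For the biomechanical outcomes that the SAP covers, its five-condition model already replaces the four-load wording in 5.6.

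**What to change.** - In Protocol 5.6, Secondary Analyses, state that the satisfaction analysis covers all five conditions (no load plus four added loads), or give the reason for leaving no load out.
- Report the comparison of feet at no load separately, beside the loaded comparisons.
- Reconcile four versus five study prostheses in the same sentence and wherever else the number differs, and define the Bonferroni family.
- State in 5.5 that the rating is also taken after the no-load walk.
- For consistency only, align the four-load list in the main part of 5.6 with 3.0 and the SAP.

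If ratings are taken as read here, no new data are needed. The statistical cost is the larger comparison family shown above, if all within-load pairs are tested. If no-load ratings are not being taken, the cost is one extra rating per foot at the second visit.
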